5.1. Pre-registration evaluation

Recruitment

Recruitment will be conducted in two main university hospitals in Lithuania. Physicians will be trained to identify potential candidates during their regular visits. Information brochures will be

provided in waiting rooms and clinics to raise awareness about the study. Additionally, potential participants might be contacted via phone or email, if they previously agreed to be informed about research opportunities.

5.2. Inclusion criteria

1. Adult patients aged between 40 and 80 years.
2. Clinical diagnosis of stable angina.
3. For Group A: A history of severe COVID-19 infection, defined as a positive polymerase chain reaction test for COVID-19 and requiring supplemental oxygen therapy for a SpO₂ < 90% on room air.
4. For Group B: No history of COVID-19 infection.

5.3. Exclusion criteria

1. Acute coronary syndromes (unstable angina, non-ST elevation myocardial infarction, or ST-elevation myocardial infarction).
2. History of myocardial infarction.
3. Ejection Fraction ≤ 40%
4. Obstructive coronary artery disease
5. History of coronary artery bypass graft surgery.
6. Severe kidney disease (eGFR <30 mL/min/1.73 m²).
7. Severe liver disease or liver function test abnormalities (aspartate aminotransferase or alanine aminotransferase levels >3 times the upper limit of normal).
8. Patients who are allergic to adenosine (since hyperemia during IMR measurement is achieved by adenosine injection).
9. Significant valvular heart disease or cardiomyopathy.
10. Patients who are pregnant or breastfeeding.
11. Patients on chronic supplemental oxygen therapy prior to their diagnosis of COVID-19 infection
12. Patients who are unable to comply with study requirements.

5.4. Withdrawal criteria

1. Participant's decision to leave the study at any time.
2. Any serious adverse event or complication related to the study procedure.
3. Development of a condition in a participant that falls under the exclusion criteria after the start of the study.

13.Clinical events

6.1. Definitions

The following definitions will be employed in this study.

Serious adverse event or complication related to the study procedure: myocardial infarction, coronary dissection, coronary perforation, stroke, retroperitoneal hemorrhage, mechanical hardware failure, anaphylactoid contrast reaction, death, or other serious complication arising directly from the study procedure.

Stable angina: Grade II or grade III angina according to the Canadian Cardiovascular Society angina grading system (6,7).

Severe COVID-19 infection: A positive COVID-19 polymerase chain reaction test in the setting of appropriate clinical symptoms, with an oxygen saturation < 90% on room air measured by pulse oximetry, requiring supplemental oxygen (8).

Myocardial infarction: Detection of an elevated cardiac troponin value above the 99th percentile upper reference limit with a rise and/or fall of cardiac troponin values with at least one of the following: symptoms of acute myocardial ischemia, new ischemic electrocardiographic changes, development of pathological Q waves, imaging evidence of new loss of viable myocardium or new regional wall motion abnormality in a pattern consistent with an ischemic etiology, or identification of a coronary thrombus by angiography including intracoronary imaging (6).

Severe kidney disease: estimated glomerular filtration rate <30 mL/min/1.73 m² by Cockcroft-Gault equation (9).

CMD is defined as either an IMR > 25 or CFR < 2.0 (3). It is further categorized as the following endotypes: 1) structural CMD (IMR > 25 and a CFR < 2.0), 2) functional CMD (IMR ≤ 25 and a CFR < 2.0), and 3) undetermined CMD (IMR > 25 and a CFR > 2.0).

6.2 Reporting procedures

Clinical Events Committee (CEC)

The CEC is made up of cardiologists who are not participants in the trial. The CEC is charged with the development of specific criteria used for the adjudication of clinical events and clinical endpoints in the trial which are based on protocol.

The CEC will establish explicit rules outlining the minimum amount of data required, and the algorithm followed in order to classify a clinical event. All members of the CEC will be blinded to the treatment arm and the primary results of the trial.

The CEC will meet regularly to review and adjudicate all clinical events in which the required minimum data is available. The CEC will also review and rule on all deaths that occur throughout the trial.

Reports of clinical events should be submitted within 15 days of the Chief Investigator becoming aware of the event.

Local investigators should report any clinical events as required by their Local Research Ethics Committee, Sponsor and/or Research & Development Office.

Contact details for reporting clinical events: [name]
Email : [contact]

Case report form

An online CRF form will be used throughout the study. This will be secure, and compatible with currently guidelines to ensure security of patient data. It will be managed via the Lithuanian University of Health Sciences Clinical Trials Unit.

7. Assessment and follow-up

Upon completion of the procedure, participants will immediately undergo vital sign monitoring, including assessments of blood pressure, heart rate, and oxygen saturation to ensure stability. A post-procedural ECG will be administered to identify any new irregularities or changes potentially induced by the intervention. Clinicians will also conduct a prompt clinical evaluation to detect any immediate complications stemming from the invasive functional assessment or a worsening of existing symptoms. Furthermore, while still on-site, patients will be requested to provide feedback regarding the procedure, detailing any discomfort or concerns they may have experienced. Lastly, for consistency and comprehensive data capture, all pertinent findings and observations from the post-procedure evaluation will be documented using a standardized data collection form.

8. Statistics and data analysis

For the successful interpretation of results derived from the COMET-19 study, the data will undergo rigorous statistical analysis. Here's a brief overview:

1. Data Management: All data collected will be entered into a secure, electronic database with backup systems in place. Double-entry methods and routine cross-checks will be implemented to minimize data-entry errors.
2. Descriptive Statistics: Basic statistics like mean, median, standard deviation, and interquartile ranges will be utilized to describe continuous variables. For categorical variables, frequencies and percentages will be used.
3. Comparative Analysis: To compare the incidence of CMD between Group A (COVID-19 with oxygen supplementation) and Group B (no history of COVID-19), a Chi-square test or Fisher's exact test will be employed for categorical variables, and the t-test or Mann-Whitney U test will be used for continuous variables, depending on the data distribution.
4. Correlation Analysis: Pearson's or Spearman's rank correlation will be used to assess the relationship between the duration of oxygen supplementation and the severity of CMD.
5. Significance Level : A p-value of less than 0.05 will be considered statistically significant for all tests.
6. Multiple Testing: Adjustments for multiple comparisons, if applicable, will be done using methods like the Bonferroni correction to prevent type I errors.
7. Missing Data: Any missing data will be addressed using suitable imputation methods. The extent and pattern of missing data will be analyzed, and if it's determined to be missing at random, multiple imputation methods may be used.
8. Subgroup Analysis: If sample size permits, further subgroup analyses might be performed to identify any trends or patterns within specific subsets of the population, such as based on age, gender, or other relevant factors.

9. Graphical Representation: Key results will be depicted using appropriate charts and graphs to aid in the visualization and interpretation of findings.

10. Software: All statistical analyses will be performed using a validated statistical software package like SPSS, R, or Stata.

11. Reporting: Results will be reported in accordance with relevant guidelines for observational studies, ensuring clarity, transparency, and reproducibility.

9. Regulatory issues

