1.1. Study summary

Design

The COMET-19 study is a prospective cohort study that aims to compare the prevalence of coronary microvascular dysfunction (CMD) in patients with stable angina who have a history of severe COVID-19 infection and those with stable angina without a history of COVID-19.

Aims

The primary aim of the study is to determine whether a history of severe COVID-19 infection impacts the prevalence of CMD and its endotypes in stable angina patients.

Outcome measures

The primary outcome measure will be the prevalence of CMD in both groups, measured by both coronary flow reserve (CFR) and index of microvascular resistance (IMR) using a pressure-temperature wire.

Population

The study population for the COMET-19 trial consists of adult patients (aged 40 -80 years) with a clinical diagnosis of stable angina. They will be recruited from two university hospitals in Lithuania: Seamen's Branch, Klaipeda University Hospital, Klaipeda, and the Hospital of Lithuanian University of Health Sciences Kaunas Clinics, Kaunas.

Eligibility

Eligible patients will be those who have been diagnosed with stable angina and are scheduled to undergo angiography and possible revascularization. The study population will be divided into two groups:

Group A: Patients with stable angina and a history of severe COVID-19 infection.

Group B: Patients with stable angina without a history of COVID-19 infection. This group serves as a comparison group to assess the potential differences in CMD prevalence.

Duration

Anticipated recruitment is 6 months. Follow-up will occur 3 months after coronary angiography

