3.1 Primary, Secondary and Tertiary Objectives

1. Primary objectives:

To determine if there is a significant difference in the prevalence of coronary microvascular dysfunction (CMD) between patients with stable angina who have had a severe COVID-19 infection (Group A) and those stable angina without a history of COVID-19 (Group B). This will be measured using both coronary flow reserve (CFR) and index of microvascular resistance (IMR) through the pressure-temperature wire.

2. Secondary Objectives:

- I. To assess the severity of CMD, as indicated by the CFR and IMR values, in both groups. This will allow for a deeper understanding of the extent of CMD in each group.
- II. To evaluate any potential correlation between the duration of oxygen supplementation (in days) in the COVID-19 group and the incidence and severity of CMD. This could provide insight into whether the length of severe illness contributes to the risk or extent of CMD.
- III. To investigate which CMD endotype (structural or functional) predominates in both groups.

3. Tertiary Objectives:

- I. To investigate the patient-reported outcomes in both groups, especially in relation to symptoms of angina, quality of life, and functional status. This would give insight into how CMD affects patients' day-to-day lives and well-being.

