3.2 Rationale for the study

The aftermath of the COVID-19 pandemic has unveiled a plethora of lingering health complications in those who have recovered, notably the 'long-COVID' or 'post-acute sequelae of SARS-CoV-2 infection' (PASC). Among these post-recovery symptoms, cardiovascular complications, especially angina-like chest pain, have surfaced as a significant area of concern. The possible mechanisms range from direct viral injury to the heart, systemic inflammatory responses, microvascular damage, to increased thrombotic events. Given this backdrop, understanding the potential link between severe COVID-19 infection and coronary microvascular dysfunction (CMD) becomes crucial, especially since CMD is known to predict adverse outcomes, such as persistent angina and heart failure, in other contexts.

Established diagnostic methods, such as the IMR and CFR measurements via a pressure-temperature wire, offer a reliable avenue to investigate this microvascular function. Currently, there is a knowledge gap regarding the long-term cardiovascular implications of COVID-19, specifically in relation to CMD. By investigating the incidence of CMD in those with a history of severe COVID-19 against those without, the study aims to ascertain whether the virus plays a direct role in the onset of CMD, providing clarity in an area currently clouded with uncertainties.

In essence, the COMET-19 study seeks to bridge the existing knowledge chasm concerning cardiovascular consequences in post-COVID-19 patients. The findings will not only provide insights into the causative relationship between COVID-19 and CMD but will also guide clinical decisions, and patient management, ultimately improving outcomes for those recovering from severe forms of the virus.

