4.1 Study overview diagram

4.2 Study protocol:

Following enrollment in the study patients should undergo the following:

Baseline assessment:

- A. Demographics:
 - Age
 - Gender
 - Center
 - Rural vs Urban
- B. Medical History:
 - History of cardiovascular diseases (specifically any known coronary artery disease)
 - History of diabetes, hypertension, or other comorbid conditions
 - Medications currently being taken
 - Past surgeries or medical interventions
- C. COVID-19 Specific History (for Group A):
 - - Date of COVID-19 diagnosis
 - - Duration of hospitalization
 - - Length of time on oxygen supplementation
 - - Any other COVID-19 related complications experienced
- D. Clinical Assessment:
 - Vital signs (Blood Pressure, Heart Rate, Respiratory Rate, Temperature, Oxygen Saturation)
 - - Body Mass Index (BMI)
 - -Physical examination focusing on the cardiovascular system
- E. Symptom Assessment:
 - Onset, frequency, duration, and severity of angina symptoms
 - Presence of any other cardiovascular symptoms (e.g., shortness of breath, palpitations)
 - New York Heart Association classification
- F. Diagnostic Tests:
 - Electrocardiogram
 - Echocardiogram or other imaging if available and relevant
 - Blood tests (cardiac markers, lipid profile, Inflammatory markers, blood glucose, blood counts and renal function panel)
- G. Patient-Reported Outcomes:
 - Quality of Life assessment, (Seattle angina score)

H. Risk Factors:

-  - Smoking history
-  - Alcohol consumption
-  - Physical activity levels
-  - Family history of cardiovascular diseases

I. Review of Previous Treatments (if any):

-  - Medications previously prescribed for angina (Trimetazidine, Ranolazine, cardiovascular related drugs)

Functional assessment

Functional assessment will be performed just after undergoing the diagnostic coronary angiography

Invasive functional assessment

- Upon intubation of the guiding catheter, 300 mcg of intra-coronary glyceryl-trinitrate will be administered to control coronary vasomotor tone.
- Coronary flow reserve (CFR), fractional flow reserve (FFR), and index of microvascular resistance (IMR) will be assessed using the CoroFlow system (Coroventis Research AB, Uppsala, Sweden).

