4.4. Relevance and Implications of the Trial Results

- Clarity in Cardiovascular Consequences: With COVID-19 known to affect multiple organ systems, including the cardiovascular system, understanding the potential long-term implications becomes paramount. Determining whether there's a direct link between severe COVID-19 infection and CMD will shed light on this critical area of uncertainty.
- Guidance for Clinical Decisions: If a significant association between severe COVID-19 and CMD is established, this could directly impact clinical decisions. It may necessitate a different approach or more frequent monitoring for COVID-19 survivors presenting with angina-like symptoms.
- Informed Patient Management: For patients who have recovered from severe COVID-19 infections, knowing the potential risks and understanding the importance of regular cardiac check-ups will be pivotal. An informed patient is better equipped to participate actively in their care and adhere to medical advice.
- Potential for Further Research: The results of this trial could set the stage for additional studies, especially focused on therapeutic interventions, management strategies, and possibly preventive measures for at-risk populations.

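### The only planned CMD comparison between two non-randomised groups is unadjusted: it answers the descriptive objective in 3.1 but cannot carry the causal wording in 1.1, 3.2 and 4.4

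*Combined protocol and SAP*

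**What the plan says.** Section 1.1 describes a prospective cohort. Section 5.2 forms the groups by history: severe COVID-19 (Group A) or no COVID-19 (Group B).

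The planned comparison is in section 8 item 3: "To compare the incidence of CMD between Group A (COVID-19 with oxygen supplementation) and Group B (no history of COVID-19), a Chi-square test". Fisher's exact test is the named alternative, with a t-test or Mann-Whitney test for continuous variables. Item 6 adjusts for multiplicity only. Item 8 allows subgroup analyses by age, gender or other factors if numbers permit. Item 11 promises reporting to observational-study guidelines. No regression, matching, weighting, pooled stratified estimate or covariate list appears.

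Section 4.2 nevertheless records "History of diabetes, hypertension, or other comorbid conditions", together with age, gender, centre, BMI and smoking.

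The stated purposes differ in strength:
- The primary objective (3.1) and primary hypothesis (3.3) concern a difference in CMD prevalence.
- The aim in 1.1 is to "determine whether a history of severe COVID-19 infection impacts the prevalence of CMD".
- Section 3.2 says that "the study aims to ascertain whether the virus plays a direct role in the onset of CMD" and that the findings will "provide insights into the causative relationship between COVID-19 and CMD".
- Section 4.4 says that settling whether there is a "direct link between severe COVID-19 infection and CMD will shed light on this critical area of uncertainty". It adds: "If a significant association between severe COVID-19 and CMD is established, this could directly impact clinical decisions".

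**The concern.** Patients who had COVID-19 severe enough to need oxygen may differ from patients who never had it in factors that also relate to CMD. The exclusions in 5.3 (prior infarction, obstructive disease, low ejection fraction, bypass surgery, eGFR below 30) narrow both groups. They do not balance diabetes, hypertension, BMI or smoking, and any age from 40 to 80 is eligible.

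If Group A carries more risk, a crude test can show a COVID-19 effect that is not there. If Group B does, it can hide a real one. Followed as written, the plan would read a crude difference as the effect of COVID-19, and 4.4 links a significant result to clinical decisions. No planned estimate separates COVID-19 from risk factors that the study has already recorded.

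**Working it through.** **1. The plan's own sample size.** Inputs: 15% and 45%, power 0.9 (4.5); significance level 0.05 (section 8 item 5); two-sided is assumed, since sidedness is not stated. With the pooled-variance formula:

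n = [1.960·√(2·0.30·0.70) + 1.282·√(0.15·0.85 + 0.45·0.55)]² / 0.30² = (1.270 + 0.785)² / 0.09 = 46.9, so 47 per group and 94 in total.

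The figure reproduces. It is the size for an unadjusted two-proportion test, with no allowance for adjustment. Exact binomial enumeration at 47 per group gives power 0.907 (chi-square) and 0.865 (Fisher). With 15% in both groups the false-positive rates are 5.5% and 2.2%.

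**2. How much confounding could do.** The documents give no risk-factor prevalences by group, so every risk-factor input here is assumed. The model has three independent binary factors (diabetes, hypertension, obesity), a common odds ratio for CMD, Group B fixed at 15% and no COVID-19 effect.

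Worked case: Group A 40/70/50%, Group B 20/50/30%, odds ratio 2.0. The shares of patients with 0, 1, 2 and 3 factors are 0.09, 0.36, 0.41, 0.14 in Group A and 0.28, 0.47, 0.22, 0.03 in Group B. The CMD risks that give Group B 15% are 7.4%, 13.7%, 24.2% and 38.9%. Group A then has 0.09·7.4 + 0.36·13.7 + 0.41·24.2 + 0.14·38.9 = 21.0%, a spurious gap of 6.0 points.

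Results at odds ratios 1.5 / 2.0 / 2.5:

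| Group A vs Group B | Spurious gap (points) | Chi-square false positives | Fisher false positives |
|---|---|---|---|
| Balanced | 0 | 5.5% | 2.2% |
| 40/60/50 vs 30/50/40% | 1.6 / 2.8 / 3.6 | 6.0 / 6.9 / 8.0% | 2.6 / 3.3 / 3.9% |
| 40/70/50 vs 20/50/30% | 3.4 / 6.0 / 7.9 | 7.7 / 12.0 / 16.8% | 3.7 / 6.8 / 10.5% |
| 45/80/60 vs 20/55/30% | 4.6 / 8.1 / 10.9 | 9.4 / 17.3 / 26.0% | 4.9 / 10.9 / 18.1% |

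The bias can also run the other way. If Group B carries the 20-30-point excess and the true adjusted gap is 30 points, the crude gap shrinks to about 26-18 points. Chi-square power then falls from 0.91 to about 0.81-0.55.

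**3. Can the study afford an adjusted estimate?** Expected CMD cases are 47·0.15 + 47·0.45 = 28.2. An outcome regression would therefore hold about 2-3 parameters at 10 cases each, or about 5 at 5 each. A propensity model fits group membership (47 vs 47), so the number of CMD cases does not limit it.

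If covariates explain a share R² of group membership, the effective size is 47(1−R²) per group. For R² = 0.05 that is 44.65 and power is Φ[(0.30·√44.65 − 1.270)/0.612] = 0.88. For R² = 0.10, 0.20 and 0.30, power is 0.87, 0.82 and 0.77. This takes the adjusted gap to be the full 30 points.

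**The case against.** The strongest reply is that the core analysis fits the core question. Objective 3.1, hypothesis 3.3, the primary outcome in 4.3 and the sample size all concern a prevalence difference, and the crude test estimates it. The firmest causal wording is in the rationale and relevance sections, and 4.4 also speaks of association. That stands, and it is why the primary test should stay. But 3.2 states the direct role of the virus as something the study aims to ascertain, and the aim in 1.1 is itself worded causally.

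Section 8 is not wholly silent either. Item 2 would describe the groups, and item 8 could yield contrasts within strata. So it would be wrong to say that the recorded factors have no possible use. Item 8 is optional, unspecified and not pooled, and item 11 names no estimate.

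A reader might infer that the missing adjustment is the whole reason the causal readings fail, so that adjusting would rescue them. The documents do not support that. Section 4.2 measures CFR and IMR once, after infection, with no earlier value, so onset stays out of reach whatever the covariates, and unmeasured confounding remains.

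Mild imbalance also does little: with 10-point differences, Fisher's test stays below 5% at every odds ratio tried.

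**Conclusion.** The point holds and should be fixed. No adjusted between-group estimate is pre-specified, and the causal wording goes beyond what the design and analysis can show. The crude primary test is valid for 3.1, and N=94 is correct for it.

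The size rests entirely on assumed risk-factor prevalences and odds ratios of 1.5-2.5. Over imbalances of 10 to 30 points with Group A higher, the spurious gap is 1.6-10.9 points, with false positives of 6.0-26.0% (chi-square) or 2.6-18.1% (Fisher). It is zero if the groups are balanced, and the sign reverses if Group B carries more risk.

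A reader might infer that a significant result would be mere confounding, or that the bias must favour a COVID-19 effect. Neither follows: no scenario in the table approaches the planned 30 points, and the documents do not show which group carries more risk.

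**What to change.** 1. Keep chi-square/Fisher as the crude primary comparison, and state that the 0.9 power applies to it alone.
2. Add one pre-specified adjusted CMD prevalence difference with a 95% CI. Use a fixed list from 4.2 (age, sex, diabetes, hypertension, BMI, smoking, centre), defined the same way in both groups and with no data-driven selection.
3. Choose a method that about 28 CMD cases do not limit. Propensity-score overlap weighting with a small-sample-corrected sandwich standard error is one example.
4. Fix the list before the 4.5 re-assessment. Leave the continue/halt rule on the crude primary comparison, and read the adjusted estimate by its interval.
5. Reword 1.1, 3.2 and 4.4 to association, adjusted where that estimate is meant, and name the single post-infection measurement and unmeasured confounding as limits.

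The cost is document wording and one extra analysis of data already collected, with no new procedure. The real price is precision: adjusted power at N=94 is about 0.88-0.77 if covariates explain 5-30% of group membership and the adjusted gap is 30 points, and lower if confounding accounts for part of the gap. The study is unfunded (9.7), and no larger N is requested.

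### The interval from COVID-19 to the CMD measurement is neither limited nor analysed, so the unadjusted oxygen-duration correlation is open to confounding by it

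*Combined protocol and SAP*

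**What the plan says.** **Entry.** Section 5.2 defines the exposed group by test result and oxygen need, without a date window: "For Group A: A history of severe COVID-19 infection, defined as a positive polymerase chain reaction test for COVID-19 and requiring supplemental oxygen therapy". The definition in 6.1 adds symptoms but no timing: "Severe COVID-19 infection: A positive COVID-19 polymerase chain reaction test in the setting of appropriate clinical symptoms". The only exclusion in 5.3 that mentions COVID-19 concerns earlier oxygen use, not time since infection: "Patients on chronic supplemental oxygen therapy prior to their diagnosis of COVID-19 infection".

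**Measurement.** Section 4.2 places the functional assessment directly after the diagnostic angiogram. Nothing ties it to the infection.

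**Data collected.** Item C of 4.2 records, for Group A, "Date of COVID-19 diagnosis" and "Length of time on oxygen supplementation". With the angiography date, the interval can therefore be derived.

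**Analysis.** Secondary Objective II (3.1) hopes to learn "whether the length of severe illness contributes to the risk or extent of CMD". Section 8, item 4 answers with a two-variable correlation: "rank correlation will be used to assess the relationship between the duration of oxygen supplementation and the severity of CMD". No item in Section 8 uses regression or any other covariate adjustment. Item 8 allows optional subgroups by unspecified further factors and does not name time since infection.

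**Stated purpose.** The rationale in 3.2 says that "there is a knowledge gap regarding the long-term cardiovascular implications of COVID-19, specifically in relation to CMD", and 4.4 also speaks of long-term consequences.

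**The concern.** A patient weeks after oxygen treatment and a patient years after it can both enter Group A and count equally in the correlation. Objective II asks an explanatory question: does longer severe illness lead to more CMD? Suppose that microvascular function changes with time since infection, and that oxygen was given for longer or shorter periods in different phases of the pandemic. The interval would then relate to both variables, and the crude correlation would carry its effect as well as that of oxygen duration. The result could be a spurious association or a masked one, and nothing in the plan would reveal which.

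If the interval relates to CMD but not to oxygen days, there is no bias. The interval then only adds unexplained variation and lowers power.

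At stake are Secondary Objective II and the second secondary hypothesis, together with how far the report can use the long-term language of 3.2 and 4.4.

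**Working it through.** **The plan's own figure.** Section 4.5 gives 15% v 45%, power 0.9, 47 per group. Significance is 0.05 (Section 8, item 5); sidedness is not stated, so two-sided is assumed here. With pooled variance and no continuity correction:

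n = [1.960 × √(2 × 0.30 × 0.70) + 1.282 × √(0.15 × 0.85 + 0.45 × 0.55)]² / 0.30² = 46.9, rounded up to 47 per group, 94 in total.

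The stated size reproduces. It was set for the primary comparison; the correlation uses the 47 patients of Group A.

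**Method for the correlation.** Let a be the correlation of the interval with oxygen days, b its correlation with CMD severity, and p the partial correlation of oxygen days with severity given the interval. Then

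crude r = p × √((1 − a²)(1 − b²)) + a × b.

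Power is by Fisher's z: atanh(r) × √(n − 3) for the crude correlation, and atanh(p) × √(n − 4) for the partial one, with n = 47, against 1.960. This is exact neither for ranks nor for skewed data, but serves for scale. Severity is signed so that higher is worse; CFR must be reversed for this.

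**Every value of a, b and p below is an assumption.** The documents give none.

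*Links of opposite sign (b = −a):*

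| a | p = 0: crude r | false-positive rate | p = 0.4: crude r | crude power | adjusted power |
|---|---|---|---|---|---|
| 0.2 | −0.04 | 5.8% | 0.34 | 0.66 | 0.79 |
| 0.3 | −0.09 | 9% | 0.27 | 0.46 | 0.79 |
| 0.4 | −0.16 | 19% | 0.18 | 0.22 | 0.79 |

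Example at a = 0.3, p = 0.4: 0.4 × 0.91 − 0.09 = 0.274; atanh(0.274) × √44 = 1.87, which gives power 0.46. Adjusted: atanh(0.4) × √43 = 2.78, which gives 0.79.

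*Links of the same sign (b = a):* the crude value is inflated. At a = 0.3, p = 0.4: 0.4 × 0.91 + 0.09 = 0.45. With p = 0 the false-positive rates equal those in the table.

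*Interval related to CMD only (a = 0, p = 0.4):* crude r = 0.4 × √(1 − b²). At b = 0.3 this is 0.38, power 0.76; at b = 0.5 it is 0.35, power 0.67; adjusted power is 0.79. The false-positive rate stays at 5%.

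**Price of adjusting.** The smallest correlation detectable with 80% power is tanh((1.960 + 0.842)/√44) = 0.399 crude and tanh((1.960 + 0.842)/√43) = 0.403 with one covariate.

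**The case against.** **Bias is not shown.** It needs the interval to be related to both variables, and the documents have data on neither link. At a = 0.1 with no true effect, the false-positive rate is about 5.1%; at 0.2 it is 5.8%. The large figures need links of 0.3 to 0.4, and the power losses also need opposite signs. This stands: a reader might infer that the correlation is confounded, and the documents do not support that.

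**Mixed intervals are what the primary objective asks for.** Sections 1.1, 3.1 and 3.3 compare patients with any history of severe COVID-19 with patients who have none. Long-term effects appear in the rationale and relevance text, not in an objective, hypothesis or outcome. This also stands. A reader might infer that the Group A prevalence is uninterpretable, or that eligibility needs a minimum interval. Neither follows: the documents define no threshold for long-term, and they give no interval distribution from which to tell how many patients a restriction would lose.

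**Adjustment cannot isolate recovery.** Recruitment is expected to last 6 months, so if infections were spread over a much longer period, the interval is nearly collinear with the calendar period of infection. This stands and limits interpretation. It does not weaken the case for adjusting, because either could distort the correlation.

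**The plan leaves room.** Section 8 calls itself an overview, item 2 would describe continuous variables, and item 8 permits further subgroups. But the subgroups are optional, the interval is not named, and none of this touches item 4. An adjustment chosen after the results are seen would be post hoc.

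**Other covariates are unused too.** Age, diabetes, hypertension and smoking are collected and also absent from item 4. That is true and is a wider gap. Nothing here shows that the interval is the most important one.

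**Conclusion.** The point holds as a gap in the analysis plan. The interval from diagnosis to measurement is not limited by eligibility and not used in any analysis, although it can be derived from a date already collected. The correlation in item 4 is therefore open to confounding by the interval, and the plan has no means to detect or remove it.

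The possible size runs from negligible to serious: a false-positive rate of 5.8% to 19% and crude power of 0.66 down to 0.22 (against 0.79) over assumed opposite links of 0.2 to 0.4. The range rests on 47 Group A patients, a two-sided 0.05 test, Fisher's approximation and, for power, an assumed partial correlation of 0.4. It illustrates the exposure and does not estimate actual harm.

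The point affects one secondary objective and the reach of the long-term wording. It does not undermine the primary comparison as stated or the sample size, and it does not call for an eligibility restriction.

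**What to change.** 1. Derive, for each Group A patient, the days from COVID-19 diagnosis to angiography, and report the distribution (median, quartiles, range).
2. In Section 8, item 4, make the analysis a partial Spearman correlation, or a rank regression, of IMR and of CFR on oxygen days, adjusted for this interval. Show the crude correlation alongside.
3. State in advance that the adjustment covers the interval and the calendar period of infection together, and that its coefficient must not be read as recovery or progression over time.
4. Limit the long-term statements that follow from 3.2 and 4.4 to the intervals actually observed. No minimum interval is needed.

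Cost: one derived variable and one degree of freedom. The detectable correlation at 80% power moves from 0.399 to 0.403, and the total of 94 is unchanged.
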